RESEARCH PROTOCOL

Date	7/20/20
Title	The influence of postoperative environment on patient satisfaction and perception of care following pelvic reconstructive surgery
Principal Investigator	[name]
Sub-Investigators	[name] MD MSc, [name] DO, [name] MD, [name] MD
Research Specialist	[name] MS,
Department	Department of OB/Gyn, Division of Urogynecology and Reconstructive Pelvic Surgery
Hatton #	17-076
NCT #	03379753

Purpose of Study

- To determine the influence of homeopathic therapies such as music therapy and images of calming nature scenes in their hospital suite following vaginal reconstructive surgery for pelvic organ prolapse on parameters of recovery such as pain, satisfaction and perception of care.
 - **Primary Aim:** To determine if patients following prolapse repair including vaginal vault suspension have decreased pain measured via a visual analog scale (VAS) on postoperative day one and just prior to discharge when exposed to the diad of music, and positive images compared to patients receiving standard care.
 - **Secondary Aims:** To determine if patients following prolapse repair including vaginal vault suspension have improved satisfaction scores and perception of care when exposed to the diad of music, and positive images compared to patients receiving standard care.

Hypothesis or Research Question

- We hypothesize that patients exposed to alternative therapies such as music, and calming nature scenes will have decreased VAS scores for pain following vaginal reconstructive surgery when compared to controls.
- We further hypothesize that patients who experience the modified post-operative environment will report an improvement in overall satisfaction when providing their

overall hospital rating and will be more likely to refer their friends to the hospital for care in the future, as measured by the HCAHPS and VAS satisfaction scores.

Background

Establishing an ideal environment to optimize healing is not a new concept. In the late 1800's, Florence Nightingale wrote about the importance of supportive spaces for patient care and recovery¹. Over the past decade, interest has grown in improving the patient experience. As part of this movement, studies have sought to evaluate the mechanisms by which the postoperative environment affects a patient's outcome and perception of healing. A report written to the Center for Health Design found over 600 studies linked to hospital environment and its affect on patient satisfaction, stress, outcomes and perception of quality². Critical to the patient experience is reducing their pain, which in turn leads to improved satisfaction. Patient satisfaction has been shown to improve adherence to care plans, reduce 30-day readmission rates and decrease overall mortality^{3,4}.

Literature review reveals efforts by both medical and design teams towards improving the experience of the patient and developing an environment that promotes healing. Changes to the physical environment have been shown to have an impact on satisfaction. These parameters have included music and art.

Considering alternative therapies, much energy has been devoted to the affect that music can have on satisfaction and pain control in the post-operative period. A recent review in the Lancet, found 73 randomized controlled trials looking at how music can aid in postoperative recovery in adults. They found that the choice of music, timing of delivery and duration of exposure varied. But the studies included, showed that music can consistently reduce pain measured by VAS scores, anxiety, analgesic utilization, and can help improve patient satisfaction with their care¹¹. Music has specifically been shown to improve VAS scores for patients following open heart surgery when subjects listened for 30 minutes on post operative day one compared to control. Furthermore, patients recovering from spine surgery who had 30 minutes of music therapy while in the hospital showed significant improvements in their VAS scores over controls¹⁵.

Building on the patient surroundings, art has been shown to improve patient's vital signs, clinical outcomes and diminished cortisol levels⁵. Having a landscape on the wall of inpatient rooms in the critical care unit has been shown to decrease opiate utilization and lead to earlier discharges⁶⁻⁸. Landscapes displayed during bronchoscopy at John's Hopkins showed significant decreases in patient VAS scores⁹. Finally, patients are more likely to refer others to seek care at facilities that display art¹⁰.

Considering the effort that is now going into improving the patient experience and developing this theory of healing spaces, there has yet to be a randomized controlled trial evaluating these alternative therapies in the urogynecologic patient population. Although each of these modalities appears beneficial, we believe that a combination of these would be even more useful. Indeed, these treatments are also relatively easy to implement without undue cost or burden to the hospital. Thus, this study seeks to apply music, and art to the post operative environment for patients recovering from major urogynecologic surgery, in an effort to determine if there is an affect on their VAS scores and satisfaction when compared to controls. We also intend to document patient perceptions of their experience.

Research Plan

- **Study Design**
 - Randomized Controlled Trial
- **Setting for the study**
 - Patients of Cincinnati Urogynecology Associates, TriHealth Inc, undergoing inpatient vaginal reconstructive surgery for pelvic organ prolapse at Good Samaritan Hospital or Bethesda North Hospital will be eligible for enrollment.
 - Subjects will be enrolled during their preoperative consent or in the preoperative holding area
 - Patients who enroll in the study will provide written informed consent
 - Following enrollment, a SNOSE will dictate to which group the patient has been randomized.

- Intervention group:

- Those patients randomized to experience a modified post-operative environment will be provided with a standard private hospital room with two portable modifications.
- They will have access to a Bluetooth capable speaker with selections of music allowing them to play music or relaxation sounds of their choosing. They will be asked to listen to a minimum of 30 minutes of music three times during their stay. Music will be played at a low enough volume to allow concurrent conversation.
- Additionally, the room will be decorated with a wall hanging image of a soothing nature landscape. The landscape will be hung on the wall near the foot of the bed throughout the participant's length of stay.

- Control group:

- Those patients randomized to experience an un-modified post-operative environment will experience a private hospital room at Good Samaritan or Bethesda North hospitals without alteration.
- On POD 1, following breakfast, patients will be asked to rate their pain using a VAS scale from 0-100 mm.
- Prior to discharge they will complete a second VAS regarding their current pain. They will also complete VAS questions regarding satisfaction and overall pain during their hospital stay.
- They will be asked two modified questions similar to the Hospital Consumer Assessment of Healthcare Providers and Systems survey (HCAHPS) to determine perception of care. A modification is necessary because these questions cannot be utilized while patients remain admitted to the hospital per federal regulation.
- They will be asked two questions regarding overall perception of care (VAS 0-100mm)

- The intervention group will also be asked regarding their appreciation of music, and the landscape as a part of their healing experience.
- At their 2 weeks postoperative follow-up appointment, they will be provided similar VAS questions for satisfaction and pain, followed by the unmodified HCAHPS questions. They will also be asked to report their overall satisfaction with the results their surgery and their decision to have surgery.
- The intervention group will be asked similar questions regarding their experience with music and landscape during their recovery.
- Demographics, medical and surgical information, complications, postoperative narcotic use, voiding trial results, CBC, etc will be recorded from their chart.
- Post-operative orders will be completed through a standardized order set which provide the standard of care for the post-operative management of patients having vaginal reconstructive surgery. There will be no differences in these orders between intervention and control group with exception of the music and landscape.

- **Participants**

- Study population: All women 18 years of age or older, who undergo vaginal vault suspension in conjunction with pelvic organ prolapse reconstruction, with or without additional concomitant procedures by a physician at Cincinnati Urogynecology Associates, TriHealth for treatment of pelvic organ prolapse (POP) will be approached for recruitment at their office visit when they sign surgical consent or at the pre-operative holding area.
- Inclusion/Exclusion criteria:
 - Inclusion
 - Adults 18-85 years of age
 - English speaking

- Undergoing surgery for pelvic organ prolapse to include an apical vaginal vault suspension by a physician at Cincinnati Urogynecology Associates, TriHealth
- Concomitant procedures such as hysterectomy, suburethral sling, anterior or posterior colporrhaphy, bilateral salpingectomy or salpingoophorectomy will be included
- Ability to complete the questionnaires and provide consent
- Willingness to listen to music at the minimum recommended time intervals
- Exclusion
 - Unwillingness to participate in the study
 - Physical or mental impairment that would affect the subject's ability to utilize the modified environment such as deafness, blindness or dementia.
 - Patients who take daily narcotics or NSAIDS
 - Patients with history of Drug or Alcohol Abuse
 - Patients with chronic pain syndromes.
 - Non English speaking
 - Patients that do not undergo a vaginal apical suspension procedure
- Sample Size
 - In the literature there does not exist a trial that has addressed these components in isolation or conjunction for patients undergoing pelvic reconstructive surgery.
 - Our sample size calculation took into account several factors, as well as our divisions' prior experience with studies evaluating pain following this surgical approach.
 - In order to represent a clinically significant change in pain when using the VAS score, studies completed in emergency medicine looking at acute pain reported that a difference in the VAS score of 9-13 mm represents a

true change^{12,13}. Other studies in gynecology has also confirmed that a difference between 10-20 mm may be clinically relevant following an intervention^{17,20-23}

- Previous studies looking at the effect of music on post-operative pain in other specialties have shown an average decrease in the VAS score of 7-26mm^{11,14-16}. These studies do however display a variety in effect and differing standard deviations.
- Review of referenced studies in a large meta-analysis published by Hole et al¹¹ produced a heterogeneous population and varied results and sample sizes.
- The most reliable statistics appear to be in a paper by Cutshall¹⁶ et al, which reported results of an intervention of music for cardiac surgery patients in the ICU. The data demonstrates a narrow standard deviation and results in agreement with overall conclusion of the meta-analysis
 - Decrease in mean pain score was 1.4cm for their music group and 0.4cm for the control group, with a difference of 10mm between the groups (SD was 1.4).
- This study was therefore selected for calculation of our sample size.
- We powered our study to detect a difference of 10mm in the postoperative VAS score between intervention and control groups. We deem this reasonable considering the review article by Hole¹¹ reporting on 73 randomized trials, found a mean overall difference in pain scores of 23mm between intervention and control groups.
- Power Analysis
 - Our calculation demonstrated need to enroll 43 patients in each arm based on the following:
 - A difference of 1cm on subjects' VAS scores for pain
 - Power at 90%
 - Standard deviation at 1.4
 - Effect size at 0.714

- Assuming an estimated loss rate of 15%, the number of patient enrollment per arm was set to 51, for a total of 102 patients. [Attrition calculation: (43/0.85)]
- This study met challenges with personnel shifts within Hatton Institute that impacted data collection. Following review, hiring of new staff and re-training, we determined to perform an interim analysis. Of the 52 subjects enrolled since restructuring, 42 have completed follow-up. This interim analysis reveals a true attrition rate of 20%; five percent higher than the original 15% used in the power calculation. Assuming this loss rate remains constant through the close of the study, in order to reach significance, we will need to enroll an additional 27 subjects above the planned 102. For sake of randomization, we have set new total enrollment to 132.
- Subjects will be randomized by using a random numbers table and sealed sequential envelopes prepared by an independent statistician.
- **Data Collection**
 - Primary outcome:
 - VAS scores for pain “right now” and “most intense pain” [0-100mm], administered following breakfast on post-operative day one, comparing intervention and control groups
 - Secondary Outcomes:
 - VAS pain scores prior to discharge based on the validated SPS pain questions²⁵.
 - VAS for satisfaction with their hospital stay prior to discharge
 - Nursing recording pain scores prior to delivery of pain medications (recorded in Epic)
 - Total morphine equivalents during hospital stay

- Patient reported impression of the music and art using Likert scales, at discharge and 2 weeks post operatively for the intervention group
- Patient impression of the hospital based on responses from modified HCAHPS questions prior to discharge on post-operative day one:
 - First Question in VAS format: “Compared to other hospitals, how would you rate this hospital”?
 - Second Question in VAS format: “How likely are you to recommend this hospital to family and friends?”
- Patient VAS scores concerning their perception of the healing environment of the hospital and whether they would choose the hospital again
- Responses at the 2 week postoperative appointment to another identical series of VAS for satisfaction and pain, questions 21 and 22 from the HCAHPS survey, a question on pelvic symptoms after surgery, and the validated Decision Regret Scale for pelvic floor disorders²⁴
- General Demographic Data
 - Age, BMI, race, history of depression, home medications, sexual activity, alcohol use, prolapse stage, procedures performed, voiding trial results, length of stay, surgical and postoperative complications, and estimated blood loss
- *VAS Score Validity:*
 - The VAS score is a well-established tool for measuring a patient’s pain level that has been in clinical practice for decades. This tool has been applied throughout the medical field as a standardized measure of pain and remains a common method of characterizing pain levels by researchers. It has been shown to be reliable in the assessment of acute pain¹⁸.
- *HCAHPS survey questions:*
 - Survey is the first national, standardized, publicly reported survey of patients' perspectives of hospital care. HCAHPS (pronounced “H-caps”),

also known as the CAHPS® Hospital Survey, is a 32- item survey instrument and data collection methodology for measuring patients' perceptions of their hospital experience. Beginning in 2002, CMS partnered with the Agency for Healthcare Research and Quality (AHRQ), another agency in the federal Department of Health and Human Services, to develop and test the HCAHPS Survey. AHRQ and its CAHPS Consortium carried out a rigorous and multi-faceted scientific process, including a public call for measures; literature review; cognitive interviews; consumer focus groups; stakeholder input; a three-state pilot test; extensive psychometric analyses; consumer testing; and numerous small-scale field tests. CMS provided three opportunities for the public to comment on HCAHPS and responded to over a thousand comments. The survey, its methodology and the results it produces are in the public domain¹⁹.

- HCAHPS question 21: "Using any number from 0-10, where 0 is the worst hospital possible, and 10 is the best hospital possible, what number would you use to rate this hospital during your stay?"
- HCAPS question 22: "Would you recommend this hospital to your friends and family?"
 - Definitely No
 - Probably no
 - Probably yes
 - Definitely yes

- Data Collection tool
- **Intervention or experimental aspect of the study**
 - Music
 - The patients will have access to a blue tooth capable audio device in their hospital rooms that can connect to their own device or one that will be provided for them. Selections of music and relaxation sounds will be

available and they will be shown how to use the device during post-operative rounds.

- Music selections will generally maintain a relaxing tempo of 60-80bpm.
- Subjects will have no limit to the amount of music they can listen to, however they will be asked to spend 30 minutes upon arrival to their room, when getting up to the chair for the first time, and following their voiding trial. At a minimum, the audio device will be turned on for the patient during post-operative rounds, and during morning rounds if they have not yet done so.

- Landscape

- Patients will have a large print of a soothing nature landscape hung on the wall near the foot of their bed. The size will approximate 24x36 inches. Each subject will have one scene in their room.
- The scenes will be hung to the wall with a removable hanger.
- Scenes were selected based on the preferences of individual surveys carried out with 86 volunteers.

- **Statistical Analysis**

- Descriptive statistics will be calculated for all continuous and categorical data. Continuous variables will be summarized as mean (SD) or median (range). Categorical variables will be presented as frequency (Percentage). The primary outcome is the VAS scores for pain in the morning of post-op Day 1 (POD 1). Student's t-test or Mann-Whitney U test (Wilcoxon Rank Sum test) will be implemented to test for significant difference in pain and satisfaction scores and narcotic use between intervention and control groups. Assumptions will be examined and appropriate parametric or non-parametric tests will be used. For categorical data, Chi-square or Fisher's exact test will be employed to test the association.

Ethical Considerations

- **Informed consent**

- Patients who agree to participate in the study will sign a written informed consent. They will be consented by one of the stated investigators or trained Research Nurse and they will receive a copy of the signed informed consent statements (ICS). A copy will be put in their medical file.
- **Privacy information**
 - Extensive efforts will be made to ensure participant confidentiality and prevent unauthorized release of personal information. Electronic study documents will be stored on a secure drive and hard copy documents stored in a locked area. Thereby, all identifying and protected health information, including name and date of birth, will be maintained in a secure area at all times, accessible by authorized personnel only.
 - All communication between staff members regarding participant data will occur via the Subject ID number only. However, identifying information will be retained in the original/source documents.
 - The participant will be logged in the Excel spreadsheet and assigned a Subject ID number. Each participant will be assigned the next available Subject ID number. Once each Subject ID number has been assigned, it will not be reassigned.
 - Study documentation, both electronic and hard copy will be stored securely for ten years and then destroyed.
- **When and how will results be disseminated?**
 - We plan for the results to be disseminated in Spring 2020 at a national meeting in the form of a poster or oral presentation. We also plan for the results to be published.

References

1. Nightingale, F. Sick nursing and health nursing. Summary. Chicago: The International Congress of Charities, Correction and Philanthropy. 1893.

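### Ratings of the hospital are pooled over two hospitals with no hospital term in the analysis; adding one is a nearly free precision gain for the secondary rating and satisfaction outcomes

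*Combined protocol and SAP*

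**What the plan says.** - **Sites.** Patients of one practice are operated on "at Good Samaritan Hospital or Bethesda North Hospital will be eligible for enrollment" (Research Plan, Setting for the study). The expected split between the hospitals is not given.
- **Outcomes about the hospital itself.** The Secondary Outcomes list includes "Patient impression of the hospital based on responses from modified HCAHPS questions prior to discharge on post-operative day one". The two items, both on a VAS, are "Compared to other hospitals, how would you rate this hospital" and "How likely are you to recommend this hospital to family and friends". Further VAS items cover the healing environment and whether the patient would choose the hospital again. At two weeks come "questions 21 and 22 from the HCAHPS survey": a 0 to 10 rating and a four-level recommendation item. The second hypothesis of the protocol rests on the rating and recommendation results.
- **Allocation.** "Subjects will be randomized by using a random numbers table and sealed sequential envelopes prepared by an independent statistician" (end of the Power Analysis). No stratification factor or separate sequence per hospital is described, and none is ruled out.
- **Analysis.** Student's t-test or the Mann-Whitney test "will be implemented to test for significant difference in pain and satisfaction scores" and narcotic use; chi-square or Fisher's exact test is used for categorical data. No covariate or stratified test appears.
- **Data.** Hospital is not among the items under General Demographic Data.

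**The concern.** Women in the same arm are rating two different institutions. The Background argues that a hospital's physical environment affects satisfaction and perceived quality, and that facility features affect willingness to recommend. On that rationale, the hospital a woman stayed in is a plausible predictor of her rating, and it is known for every patient.

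An unadjusted comparison leaves any difference between the hospitals in the error term. What is at stake is precision on the outcomes behind the second hypothesis. These are secondary, and the sample size was not set for them, so precision that costs almost nothing is worth having.

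**Working it through.** **1. The plan's own figure.** Inputs from the Power Analysis: difference 1 cm, SD 1.4 (taken as cm), power 90%. Alpha is not stated; two-sided 0.05 is assumed. Effect size = 1/1.4 = 0.714. The two-sample t-test needs 42.2 per arm, rounded up to 43, and 43/0.85 = 50.6, rounded up to 51. Both stated figures reproduce. They concern pain; no rating outcome has a sample-size calculation.

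**2. Evaluable patients.** The revised enrolment of 132 with the stated 20% loss gives 132 × 0.80 / 2 = 52.8, about 53 per arm.

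**3. Assumptions not in the documents.** Within-hospital SD of a rating 20 mm; arm effect 10 mm; hospital gap D from 5 to 20 mm; share p of patients at one hospital 0.5 or 0.8.

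**4. Formula.** Unadjusted variance = 20² + p(1 − p)D². With p = 0.5 and D = 10 this is 400 + 0.25 × 100 = 425, or 6% more than 400. Power is that of the two-sided t-test at 0.05 with 53 per arm and the resulting SD. With D = 0 it is 72.2%, which is also approximately the power with a hospital term.

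| Hospital gap D | Variance increase, p = 0.5 | Power, p = 0.5 | Variance increase, p = 0.8 | Power, p = 0.8 |
|---|---|---|---|---|
| 5 mm | 1.6% | 71.6% | 1.0% | 71.8% |
| 10 mm | 6% | 69.6% | 4% | 70.6% |
| 15 mm | 14% | 66.6% | 9% | 68.5% |
| 20 mm | 25% | 62.6% | 16% | 65.8% |

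**5. Chance imbalance is the same cost, not a second one.** The 95% range of the shift in the arm difference from hospital imbalance is 1.96 × √(2p(1 − p)/53) × D. For p = 0.5 and D = 10 mm it is ±1.90 mm. The half-width of the 95% interval for the arm difference is 1.96 × √(2 × 400/53) = 7.61 mm without the gap and 1.96 × √(2 × 425/53) = 7.85 mm with it. Since 7.61² + 1.90² ≈ 7.85², the wider interval already contains the shift.

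**6. Validity and recovery, by simulation.** 8,000 trials per scenario, 43 per arm, even split, effect 0.714 SD, hospital gap of 0.5 or 1.0 SD:

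| Quantity | Gap 0.5 SD | Gap 1.0 SD |
|---|---|---|
| Unstratified allocation, unadjusted: type I error | 5.1% | 5.2% |
| Unstratified allocation, unadjusted: power | 88.8% | 83.0% |
| Unstratified allocation, hospital term: power | 90.2% | 89.8% |
| Stratified allocation, unadjusted: type I error | 4.3% | 3.0% |
| Stratified allocation, hospital term: power | 91.1% | 90.1% |

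The mean error of the unadjusted estimate is about zero. In the roughly 16% of unstratified trials where the hospital share differs between arms by at least 15 percentage points, unadjusted type I error is 7.3% or 10.5%; with a hospital term it is 5.2% or 4.5%.

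**The case against.** The strongest case against is that nothing here is an error. The planned tests are valid. The documents contain no evidence that the hospitals are rated differently, and several facts point toward similarity: one practice, private rooms at both sites and one standardised postoperative order set. A 5 mm gap costs under one point of power; visible losses need gaps of 15 to 20 mm, and an uneven split reduces them. All of this stands, and it makes this a conditional improvement. It does not remove the case for a hospital term, because a shared order set aligns clinical orders without making buildings, nursing or reputation the same.

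Three stronger readings are tempting, and the documents support none of them.

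- *The arm comparison is biased by hospital.* A reader might infer this from the missing hospital term. Imbalance arises only by chance, the average error is about zero, and overall type I error stays near 5%. The higher conditional error applies only to trials with a notable imbalance.
- *Randomisation was unstratified.* The protocol is silent. The statistician who prepared the envelopes may have used a separate sequence for each hospital.
- *The primary result is at risk, or hospital is the main source of variation in the ratings.* No hospital effect on postoperative day 1 pain is argued anywhere. On the plan's own SD of 14 mm with 53 per arm, even a gap of 1 SD leaves about 90% unadjusted power, against 95% with none. No figure ranks the sources of variation in the ratings.

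**Conclusion.** The point holds as a nearly free improvement for the secondary outcomes that rate the hospital or the stay. The planned tests are sound but leave recoverable precision unused if the hospitals' usual ratings differ. Under the stated assumptions and an even split, the loss is under 1 point of power at a 5 mm gap, about 3 points at 10 mm, 6 at 15 mm and 10 at 20 mm. With an 80/20 split it is about 0 to 6 points. The true gap, rating SD and split are unknown, so the actual loss could be negligible. The primary pain analysis and its sample size are not called into question on this ground.

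**What to change.** 1. Record the hospital for each patient. It is not in the listed data but should be recoverable from the chart.
2. Before outcomes are compared between arms, prespecify a linear model with arm and hospital for the hospital-rating (including HCAHPS question 21), recommendation, healing-environment, choose-again and satisfaction scores. If a rank test is used, name the van Elteren test stratified by hospital.
3. For HCAHPS question 22, which has four ordered levels, specify the Cochran-Mantel-Haenszel row-mean-score test stratified by hospital.
4. Leave the envelopes unchanged and state whether they were stratified by hospital. If they were, the hospital term is still needed, because the unadjusted test would be conservative.
5. Treat adjustment of the primary day 1 pain comparison as optional, and state the choice in advance.

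The cost is one data field, a few lines in the analysis section and one degree of freedom. No patients, procedures or envelopes change. Prespecifying also prevents a later choice between adjusted and unadjusted results.

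### The 20% attrition rate is not shown to be loss of the POD 1 pain score, and even at face value it supports a total of 108, not 129 or 132

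*Combined protocol and SAP*

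**What the plan says.** The Power Analysis section states: "Our calculation demonstrated need to enroll 43 patients in each arm based on the following". The listed inputs are "A difference of 1cm on subjects' VAS scores for pain", power of 90%, "Standard deviation at 1.4" and "Effect size at 0.714". An assumed 15% loss then takes 43 to 51 per arm (43/0.85), 102 in total.

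The same section reports an interim look after staffing changes that had affected data collection: "Of the 52 subjects enrolled since restructuring, 42 have completed follow-up". It continues: "This interim analysis reveals a true attrition rate of 20" per cent. Taking that rate as constant to the end of the study, it adds 27 subjects to the 102 and then sets the total at 132 for the sake of randomisation.

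Three other places bear on how to read that count:

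- Setting for the study: "Subjects will be enrolled during their preoperative consent or in the preoperative holding area". A woman can therefore be enrolled some time before surgery.
- Research Plan, study procedures: the word follow-up is used for the appointment 2 weeks after surgery.
- Data Collection, Primary outcome: the pain VAS is "administered following breakfast on post-operative day one, comparing intervention and control groups". The Statistical Analysis section also names the POD 1 morning score as primary.

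**The concern.** There are two separate weaknesses.

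**The rate.** It is a snapshot of enrolled minus completed, taken while recruitment continued. In such a snapshot, women whose operation or 2-week visit has not yet come round look the same as women who have dropped out. A woman who gave her POD 1 score and then missed the 2-week visit is also counted as lost, although she contributes fully to the primary comparison. The plan gives no reasons for the 10 non-completions and does not define completed follow-up.

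**The step from the rate to the target.** A 20% loss rate is the only reason stated for enrolling more women, but an extra 27 does not follow from it.

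At stake is whether up to 30 further women (132 - 102) are needed for the power the plan asks for. Patients, staff time and a trial already behind its dissemination date would carry any excess.

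**Working it through.** **Inputs (all from Power Analysis).** Difference 1 cm, SD 1.4 cm, power 90%, 43 per arm; 15% loss giving 102; 52 enrolled and 42 complete; 20% loss; +27; 132. The listed inputs give no significance level, so two-sided 0.05 is assumed.

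**1. Reproduce the plan's starting figures.** For a difference of 1 and SD of 1.4, the two-sample t-test needs 42.2 per arm, so 43 (the normal approximation gives 42). Then 43/0.85 = 50.6, so 51 per arm and 102 in total. Both match.

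**2. Reproduce the rate.** (52 - 42)/52 = 10/52 = 19.2%, rounded in the plan to 20%. The exact 95% interval is 9.6% to 32.5%, which contains the original 15%.

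**3. Apply the plan's formula to its own 20%.** 43/0.80 = 53.75, so 54 per arm and 108 in total. The increase is 108 - 102 = 6. The plan's +27 gives 129, which leaves 129 - 108 = 21 unexplained; for 132 the gap is 24.

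**4. Loss rate that the target would need.** 1 - 86/129 = 33.3% for 129, and 1 - 86/132 = 34.8% for 132. Both lie above the 20% stated and above the upper limit in step 2.

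**5. How far the rate could move.** Let x of the 10 non-completers truly lack a POD 1 score, and assume all 42 completers have one. If the other non-completers already have a score, loss is x/52. If they are pending, loss is x/(42 + x). The total is 2 x ceil(43/(1 - loss)).

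| x | Others already scored | Total | Others pending | Total |
|---|---|---|---|---|
| 0 | 0% | 86 | 0% | 86 |
| 3 | 5.8% | 92 | 6.7% | 94 |
| 5 | 9.6% | 96 | 10.6% | 98 |
| 7 | 13.5% | 100 | 14.3% | 102 |
| 8 | 15.4% | 102 | 16.0% | 104 |
| 10 | 19.2% | 108 | 19.2% | 108 |

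The documents do not give x, so this is a range and not an estimate. It runs from 86 to 108.

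**6. What the totals deliver at 20% loss.** The power pairs are the t-test and the normal approximation.

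- 102 enrolled: 102 x 0.80 = 81.6, about 41 per arm, power 89.2% to 89.9%.
- 132 enrolled: 132 x 0.80 = 105.6, about 53 per arm, power 95.4% to 95.7%.

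**7. Possible sources of the 27.** Two can be constructed, and neither is documented.

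- Inflating the already inflated 102 gives 102/0.80 = 127.5, so 128. This is close to 129 but counts loss twice.
- If L earlier subjects were unusable, 0.80 x (129 - L) = 86 gives L = 21.5. The same sum for 132 gives 24.5.

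**The case against.** A reader might infer that 20% is the wrong loss rate, or at least an upper bound on it. The documents support neither.

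- They report no pending subjects and no non-completer with a POD 1 score. If all 10 were lost before POD 1, 19.2% would be right. Reading follow-up as the 2-week visit is reasonable but remains an inference.
- A woman could attend at 2 weeks and still have no POD 1 score, so POD 1 loss could exceed 10/52.
- The 52 exclude everyone enrolled before the restructuring, when data collection was disrupted, so loss over the whole trial may be higher.

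A reader might also infer that the raised target rests on an inflated rate. It does not: of the 30 added subjects, only 6 follow from 20% loss, and the other 24 would be unexplained even if 20% were exact.

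It is also fair to say that planning on full completers is cautious, since several secondary outcomes are collected at 2 weeks. The stated Primary Aim adds a VAS just before discharge, but that too is an in-hospital measure and does not make 2-week completion the relevant rate. Restricting the estimate to the restructured period is defensible for projecting future loss. Finally, about 21 unusable earlier subjects would reconcile 129 with 43 per arm, so over-enrolment is possible rather than proven.

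All of this limits the claim. It does not supply the missing counts or the derivation of 27.

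**Conclusion.** The point holds as a finding that the target is unsupported. The 20% is a non-completion rate at an interim look during open enrolment. The plan does not show that it is the loss rate for the POD 1 pain VAS, on which the 43 per arm is based. Separately, and more firmly, 20% in the plan's own formula gives 108, so neither 129 nor 132 follows from it.

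The size is 24 subjects between 108 and 132 with no stated basis, plus a smaller uncertainty about the rate itself, which could place the total anywhere from 86 to 108. That range assumes that all 42 completers have a POD 1 score and takes no account of unusable earlier data. The power figures assume two-sided 0.05.

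The consequence is possible over-enrolment and a target that cannot be audited. There is no bias and no loss of power. At 20% loss even the original 102 would give about 89% to 90% power.

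**What to change.** All of this comes from existing records and a short correction to the Power Analysis section.

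1. Define completed follow-up, and state how many of the 10 non-completers are pending and how many have a POD 1 VAS.
2. Compute POD 1 loss as subjects without a POD 1 VAS divided by randomised subjects who have reached POD 1, with pending subjects in neither count. Report it separately for before and since the restructuring. List on its own line anyone who left definitively before POD 1, because she still counts against an enrolment target.
3. Restate the total as 2 x ceil(43/(1 - loss)), using the since-restructuring rate for projection and adding explicitly any unusable earlier subjects. Alternatively, keep 132, state the power it actually delivers, and show how 27 was derived.
4. Report 2-week loss separately, among women whose visit window has closed, for the 2-week outcomes.

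The cost is a recount and a few corrected sentences. The target may fall, or it may stand with a stated reason if the recount shows higher loss or unusable earlier data.
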